483 To mitigate risk associated with loss of confidentiality, we have ensured that all procedures and data storage
484 methods are secure. Access to data is restricted to research staff on an as-needed basis, research staff are trained
485 regularly in confidentiality and privacy issues, research staff participate in weekly supervision, and quality assurance
486 checks are conducted annually.

493 Research Monitor.

494 [name], D.O. will serve as the DoD Independent Research Monitor. The duties of the research monitor shall
495 be determined on the basis of specific risks or concerns about the research. The research monitor may perform
496 oversight functions (e.g., observe recruitment, enrollment procedures, and the consent process for individuals,
497 groups or units; oversee study interventions and interactions; review monitoring plans and UPIRSTO reports; and
498 oversee data matching, data collection, and analysis) and report their observations and findings to the IRB or a
499 designated official. The research monitor may discuss the research protocol with the investigators, interview human
500 subjects, and consult with others outside of the study about the research. The research monitor shall have authority
501 to stop a research protocol in progress, remove individual human subjects from a research protocol, and take
502 whatever steps are necessary to protect the safety and well-being of human subjects until the IRB can assess the
503 monitor's report. Research monitors shall have the responsibility to promptly report their observations and findings to
504 the IRB or other designated official.

505
506 **8.2 Potential Benefits.** Potential benefits of participation in this study may include a reduction in self-injurious thoughts
507 and behaviors and PTSD symptoms over the course of therapy. Our primary goals are to treat participants to reduce long
508 term suicide risk and to the point of symptoms reduction below the level of diagnostic criteria for PTSD. In addition, the
509 knowledge gained from this study will serve to inform the most effective early interventions for the prevention and
510 treatment of suicide risk and PTSD.

511
512 **8.3 Alternatives.** Mental health treatment for both suicidality and PTSD is available via video telehealth at CRDAMC
513 through the Department of Behavioral Health (DBH) including various forms of psychotherapy and drug treatments.
514 Service members and veterans can access treatment for suicide risk and PTSD from the DBH as well as through Army
515 One-Source and may be eligible for care at one of the Veterans Healthcare System facilities or clinics. Not participating
516 in the study is also an alternative.

517
518 **9.0 ADVERSE EVENTS, UNANTICIPATED PROBLEMS, AND DEVIATIONS**

519
520 **9.1** Adverse Events will be assessed and monitored according to the established STRONG STAR SOP and the IRB of
521 record's policies and procedures.

522
523 **9.2 Reporting Adverse Events, Unanticipated Problems Involving Risks to Subjects or Others (UPIRSOs), and**
524 **Deviations to the Office of the IRB.** All adverse events, unanticipated problems involving risk to subjects or others,
525 and deviations will be reported to the Institutional Review Board (IRB) in accordance with current IRB policy. UPIRSOs
526 and recurrent non-compliance with study procedures will be reported promptly to the IRB. All adverse events that do not
527 meet the UPIRSO criteria and deviations that are not non-compliance will be summarized at Continuing Review per the
528 IRB of record's policy.

529
530 **10.0 WITHDRAWAL FROM STUDY PARTICIPATION**

531
532 Participants may withdraw themselves from this study at any time and for any reason. Withdrawal from this study
533 does not affect the participant's eligibility for care or any other benefits to which entitled. Participants who request to
534 discontinue treatment, but who do not choose to withdraw from the study completely, will be asked to return for the
535 post-treatment assessments. If a participant stops attending treatment sessions without notifying research staff, the
536 therapist or project coordinator will make diligent attempts to contact the person to evaluate their status, attempt to
537 re-engage them in the treatment, and encourage them to complete follow up assessments. Research staff will also
538 refer to appropriate outside resources if necessary. Investigator may choose to withdraw a participant after
539 consultation with the treating therapist and other consultants as appropriate in instances not limited to:

540 • Patient is noncompliant with treatment requirements
541 • Patient is in need of more intensive treatment
542 • Patient's symptoms worsen significantly
543 • Patient experiences a serious adverse event that is clearly related to the treatment
544 • Unexpected unavailability of a treating therapist

545
546 **11.0 REFERENCES**

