 136 sessions, based on therapist judgment to support good end state functioning and treatment goals to reduce PTS
 137 symptoms.

138
 139 Telehealth is an essential and safe mode of delivering mental health services, to include the delivery of exposure-
 140 based PTSD treatment^{17, 18}. Telehealth is broadly defined as behavioral health services that are delivered via
 141 communication technologies including telephone and clinical video teleconferencing. Because of the physical
 142 distancing recommendations in place with the COVID-19 pandemic, all assessment and treatment sessions for this
 143 study will occur using a computer or tablet talking over a secure line in real-time with the research staff using a
 144 computer in his or her office. The video telehealth platform used for these communications is HIPAA-compliant.
 145 While participants are in care at the CRDAMC inpatient unit, the computer or tablet will be provided by the staff to
 146 use for study procedures only. For sessions or assessment that occur after participants are discharged from inpatient
 147 care, participants will need to use a computer with high speed internet access (e.g., broad-band internet connection
 148 of at least 384kbps at 720 pixels) to support the telehealth platform. The computer must be equipped with speakers
 149 or a standard headphone jack to be able to hear and speak with the research staff. Participants will also need to
 150 have access to a private location with the ability to control access during assessment and treatment sessions to
 151 ensure your privacy and confidentiality. If participant does not have access to a computer in a private location, they
 152 can come to the STRONG STAR offices located at the Shoemaker Center on Fort Hood and use a computer in one
 153 of our offices

154

[figure not shown]
155 **6. RESEARCH DESIGN**

156

157 The proposed randomized controlled trial will examine the efficacy of the WET-S + TAU compared with TAU alone
 158 among high-risk, suicidal service members and veterans with PTSD or PTSS admitted to the CRDAMC acute
 159 inpatient psychiatry unit for suicide risk. Assessment and treatment session will be delivered via a HIPAA compliant
 160 video telehealth platform. The design overview of the study is summarized in Figure 1.

161

162 Figure1. Study Design Overview.

171
172
173
174
175
176

Posttreatment
Administration of self-report measures

177
178
179
180
181

1-Month Follow-Up Assessment

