7. RESEARCH PLAN

7.1 Selection of Subjects

- Target enrollment (number consented): 140
- Target number randomized: 124

7.1.1. Subject Population. Active duty military service members and veterans admitted to the CRDAMC inpatient psychiatry unit for treatment for suicidal thoughts or behaviors and PTS. The study will use a continuous enrollment process to allow for maximum flexibility in meeting individual patient/participant scheduling needs. Active duty service members will have priority for being enrolled in the study.

197

7.1.2. Source of Research Material. Interviews, self-report questionnaires, medical record review.

198

7.1.3. Inclusion and Exclusion Criteria.

Inclusion Criteria

1. Active duty military service member, veteran, or and DEERS eligible beneficiary (age 18- 65 years) hospitalized at Carl R Darnall Army Medical Center (CRDAMC) for non-suicidal self-injury, suicide thoughts, suicide plan or attempt confirmed by CRDAMC inpatient admission documentation.
2. PTSS of at least moderate severity (total scores > 20) confirmed by the CAPS-5.
3. Speak, read, and write English.

208

Exclusion Criteria

1. Active psychosis.
2. The presence of moderate to severe cognitive impairment (as determined by the inability to comprehend the baseline screening questionnaires).
3. The presence of any clinically significant factor that may impair an individual's ability to comprehend and effectively participate in the study, e. g., the presence of extreme agitation or violent behavior.

215

7.1.4. Description of the Recruitment and Prescreening Process. Under a waiver HIPAA Authorization for screening, study staff will collaborate with CRDAMC staff to identify potential participants who have been admitted for suicide thoughts and/or suicidal behaviors and that have symptoms of PTS as documented as part of the admission assessments.

220

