360 expectations in this yet unstudied population, we powered the study to detect small to medium sized effects for the group
361 by time interaction. Power was estimated using Repeated Measures and Sample Size computer software, accessible at
362 <https://rmass.org>. Assuming subject level randomization, a quadratic design matrix for the time effect, a 1-tailed alpha
363 level of .05, desired power of .80, equal sized treatment groups at baseline, an overall expected 15% attrition rate, a
364 stationary AR1 error correlation matrix starting at a modest $r = .30$, and desire to be able to detect at least a conventional
365 small to medium sized effect ($d = .35$) at the final assessment, the desired total sample size we intend to recruit is $N = 124$
366 ($n = 62/\text{group}$), a feasible recruitment goal given the targeted population.
367

368 **7.4.2 Primary (i.e., primary outcome variables) and secondary endpoints.** The primary dependent variables for suicidality
369 are the Self-Injurious Thoughts and Behaviors Interview (SITBI) interview and the Depression Symptom Index-Suicidality
370 Subscale (DSI-SS) self-report. The primary dependent variables for PTS symptoms and PTSD are the Clinician
371 Administered PTSD Scale (CAPS-5) interview and the PTSD CheckList-5 (PCL-5) self-report. Secondary endpoints
372 include associated psychopathology (severity scores on measures of depression, general anxiety, anger, and PTSD-
373 related cognitions)
374

375 **7.4.3 Data Analyses.** To examine hypothesis 1 (determine if WET-S + TAU reduces presence (past month), frequency,
376 and severity of suicidal ideation, suicide plans, suicide gestures, suicide attempts, and non-suicidal self-injurious
377 behaviors and re-hospitalizations related to suicidality relative to TAU only and hypothesis 2 (determine if WET-S + TAU

378 reduces PTS symptom severity relative to TAU only) , we will conduct intent-to-treatment (ITT) analyses including all
379 randomized participants who attend at least the first therapy session. General or Generalized Linear Mixed Effects
380 models, depending on the nature of the specific outcome, will be implemented for the primary ITT randomized
381 comparison of total CAPS-5 scores as well as SITBI variables of interest and number of subsequent inpatient
382 hospitalizations for suicidal behavior. The planned statistical design includes fixed effects for treatment (between-

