383 groups), time (within-subjects), and the group by time interaction. This latter effect captures differences in changes over
384 time between the groups; as such it is the effect of substantive interest in each of the models that will be examined.
385 Advantages of the general(ized) linear mixed effects model include the ability to include cases with missing data
386 (assumed missing at random), flexible specification of the covariance structure among the repeated measures, the ability
387 to model nonlinear trajectories of change over time, and the ability to perform between- and within-groups contrasts both
388 at and across assessments to examine significant group by time interactions. Prior to performing statistical analyses, the
389 data will be inspected to determine the advisability of scale transformation to normalize distributions (where applicable)
390 or reduce variance heterogeneity and to identify missing data, outliers, or other unusual features that may be influential.
391 To test hypothesis 3, growth curve modeling will be used to examine mediation. Specifically, treatment condition will be
392 entered as a predictor of change in both PTS symptom severity and suicide related outcomes. To achieve mediation,
393 WET-S +TAU would achieve superior reductions in suicide related outcomes and PTS symptom severity relative to TAU
394 only. Finally, we will examine the indirect effect of treatment condition on suicide related outcome change via PTSD
395 symptom change. Identification of an indirect effect would allow us to conclude that WET-S + TAU's superior effect on
396 suicide risk relative to TAU only is mediated by changes in PTS symptoms.
397

398 **7.7 Confidentiality.** All video telehealth therapy sessions and interview assessments will be conducted in private offices
399 in the CRDAMC acute inpatient psychiatry unit and then via video telehealth from a private location of the participant's
400 choosing once the participant is discharged from inpatient care. All assessment interviews and WET-S treatment
401 sessions speaking with the therapist will be recorded using an audio-recorder external to the HIPAA compliant telehealth
402 platform. Recordings will be labeled with the participant's study ID number.
403 The recordings will be uploaded to a secure password protected server immediately after the session is completed. The

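### Past-month suicidal ideation is probably near ceiling at baseline, so the group-by-time test in 7.4.3 is a weak, possibly non-estimable, test of this one binary outcome

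*Combined protocol and SAP*

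**What the plan says.** Inclusion criterion 1 in 7.1.3 takes patients hospitalized "for non-suicidal self-injury, suicide thoughts, suicide plan or attempt confirmed by CRDAMC inpatient admission documentation". Section 6 describes the population as "among high-risk, suicidal service members and veterans with PTSD or PTSS admitted to the CRDAMC acute" inpatient unit. Under 7.1.5 and 7.1.6, consent is obtained on the unit and the baseline interviews follow it.

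For hypothesis 1, section 7.4.3 asks whether the treatment "reduces presence (past month), frequency" and severity of ideation and the other suicide-related outcomes. The models are "General or Generalized Linear Mixed Effects" models, chosen by type of outcome. The link for a binary item is not stated.

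Of the group-by-time interaction, 7.4.3 says that "it is the effect of substantive interest in each of the models that will be examined". Time coding is left open: the listed advantages of the model include the ability "to model nonlinear trajectories of change over time, and the ability to perform between- and within-groups contrasts both" at single assessments and across them. The stated purpose of those contrasts is to explore an interaction that is already significant. The only time coding named anywhere is quadratic, in the sample-size paragraph (7.4.1).

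Hypothesis 1 runs from pre-treatment to 1 and 4 months. Figure 1 shows only self-report measures at post-treatment, so the SITBI interview has three visits.

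**The concern.** The entry rule selects on the event that the outcome records. Inpatient stays are typically short (section 4), so a past-month window at baseline should normally cover the crisis that led to admission, and most participants will answer yes. A group-by-time test asks whether the arms changed differently from baseline. On the log-odds scale, a baseline cell with almost no negative answers carries very little information, and one with none has no finite log-odds. The interaction then takes most of its variance from the few people without ideation at baseline, and not from follow-up, where the treatment effect would show.

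Ideation is the first outcome named in Aim 1. As the plan stands, a real difference in ideation at follow-up could be reported as no group-by-time effect, or the model could fail to converge, because of how patients were selected.

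**Working it through.** **The plan's own figure.** The documents give no power figure for presence of ideation. The stated N = 124 is for a continuous effect of d = .35, and I could not reproduce it from its listed inputs. A simple two-mean formula gives 4 × (1.645 + 0.842)² / 0.35² ≈ 202, or 238 after dividing by 0.85. The visit count and effect shape used in the software are not given, so this does not show that 124 is wrong. Nothing below depends on it.

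**Inputs from the documents.** 62 per arm; 15% attrition, so 62 × 0.85 ≈ 53 per arm at 4 months; one-sided .05.

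**Assumptions.** Past-month ideation at 4 months of 50% on TAU and 25% on WET-S; a common baseline presence p; within-person correlation ignored. The documents supply none of these. The nearest figure is in section 5: after WET in a previous sample, roughly half of those with ideation at baseline no longer had it 60 weeks later.

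**Step 1: how many people carry the baseline information.** The expected number per arm without ideation is 62(1 − p). The chance that at least one arm has none is 1 − (1 − p⁶²)².

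- p = 98%: 1.2 people, 49%
- p = 97%: 1.9 people, 28%
- p = 95%: 3.1 people, 8%
- p = 90%: 6.2 people, 0.3%
- p = 70%: 18.6 people, about 0%

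**Step 2: logit scale, time as categories.** The log odds ratio is ln 3 = 1.099.

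- Follow-up contrast alone: variance 1/(53 × .5 × .5) + 1/(53 × .25 × .75) = 0.176, SE 0.42. Power = Φ(1.099/0.42 − 1.645) ≈ 83%. The usual two-proportion formula gives 85%.
- Interaction: add 2/(62 p(1 − p)) to that variance.

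| Baseline presence | Interaction variance | Ratio to follow-up contrast | Interaction power |
|---|---|---|---|
| 100% | not finite | – | not estimable |
| 99% | 3.434 | 19.5 | 15% |
| 97% | 1.285 | 7.3 | 25% |
| 95% | 0.855 | 4.9 | 32% |
| 90% | 0.534 | 3.0 | 44% |
| 70% | 0.330 | 1.9 | 61% |

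Simulating the same four cells with a likelihood-ratio test gave 0%, 17%, 28%, 33% and 44% at 100%, 99%, 97%, 95% and 90%, against 85–86% for the direct comparison.

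**Step 3: with within-person correlation.** I simulated a random-intercept logistic model with visits at 0, 1 and 4 months, 62 per arm and 15% attrition. Assumed follow-up rates were 30% and 50%, the random-intercept SD was 1.5, and tests were two-sided at 5%, with 700 runs per setting. Quadratic time over three visits is saturated, so it is equivalent to categorical time.

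| Baseline presence | Group-by-time, categorical | Group-by-time, linear | Categorical runs with divergent coefficients |
|---|---|---|---|
| 100% | 2% | 15% | 100% |
| 98% | 12% | 18% | 50% |
| 95% | 18% | 23% | 7% |
| 90% | 25% | 25% | 0.3% |
| 70% | 43% | 32% | 0% |

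Comparing the arms at 1 and 4 months with a common baseline had 66% to 73% power at every baseline rate. With no true effect it rejected in 4.1% to 7.0% of runs (Monte Carlo SE about 0.8 points). At 100% baseline with categorical time, the group main effect absorbs a constant treatment effect, and the interaction sees only a difference between 1 and 4 months. Linear time keeps the interaction finite, but it is weak and, at 100% baseline, very conservative (0.6% false positives).

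**Step 4: risk-difference scale.** With the Step 2 assumptions, variance = (.25 + .1875)/53 + 2p(1 − p)/62. For a difference of .25, power is about 87% at p = 100%, 83% at 97% and 76% at 90%. The collapse belongs to the log-odds scale.

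**The case against.** The strongest reply is that the documents fix none of the conditions behind the worst figures. Criterion 1 lists self-injury without suicidal intent as a route of its own, ideation is not itself required, and no baseline rate is given. At 70% presence about 19 people per arm would be without ideation, which is not a handful. The link is unstated, and on the risk-difference scale little is lost. Linear time keeps the test estimable. Section 7.4.3 also provides for contrasts at single assessments and for inspecting the data beforehand, so an empty cell would be noticed. All of this stands as a limit on the size of the problem.

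It does not remove the problem. The at-assessment contrasts are offered only after a significant interaction, and that interaction is the step likely to fail. Inspection would reveal a ceiling, but the plan does not say which test would then decide, so the choice would be made with the data in view. Logit is the conventional link for a binary mixed model, and on that scale the interaction is clearly weaker than the direct comparison even at 70%.

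A reader might infer that the interaction is bound to be inestimable or to have zero power. The documents do not support that: it needs exactly 100% baseline presence (or an arm that happens to have no one without ideation), a logit link and categorical time. A reader might also infer that Aim 1 as a whole cannot be tested. That does not follow either. Frequency, severity, the DSI-SS (a graded ideation scale and a named primary variable), CAPS-5 and rare events such as attempts are not held at this ceiling by the entry rule.

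**Conclusion.** The concern holds in a limited form. Baseline past-month ideation is probably close to ceiling by selection, and the plan makes group-by-time decisive for it. On the logit scale with categorical or three-visit quadratic time, the test is not estimable at 100% baseline presence. It has roughly 15% to 44% power for presence between 99% and 90%, where a direct comparison at 4 months has about 83–85%.

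These figures rest on assumed follow-up rates of 50% and 25%, 62 and 53 per arm, one-sided .05 and independence within person. The mixed-model check with 30% against 50% shows the same pattern. High baseline presence is an inference from the entry rule and the timing of baseline, not a documented rate. The point covers binary ideation presence and any other SITBI presence item at a baseline ceiling. It is a should-fix: it touches one facet among several, and settling it is cheap.

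**What to change.** In 7.4.3, for binary past-month presence of ideation (and any other SITBI presence item at a baseline ceiling):

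- Make the between-arm contrast at 1 and 4 months the decisive test, not conditional on a significant interaction. State whether it is one joint test or which visit leads.
- Estimate it with a likelihood-based logistic mixed model, on the follow-up visits or with a common baseline for both arms, adjusted for baseline ideation severity.
- State the link and the time coding.
- Keep group-by-time for outcomes whose baseline is free to vary.

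Reconcile the SITBI recall period. Section 7.4.3 says past month, while section 15 has participants answer over their lifetime. On a lifetime window presence cannot fall at any visit, so the contrast needs past-month answers.

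The analysis change takes a few sentences and needs no new visits or patients. Whether it needs any change in data collection depends on whether past-month answers are already recorded. The result becomes an arm difference at each visit and not differential change, a small loss in a randomized comparison. If GEE is used instead of the mixed model, it needs a stronger missing-data assumption or weighting, which matters with 15% attrition expected.

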404 recording will then be deleted from the recorder. Study staff will be responsible to upload the audio-recording as soon as
405 possible and then deleting the recording from the audio-recorder.
406

407 **7.7.1 Certificate of Confidentiality.** We are not seeking a Certificate of Confidentiality.
408

409 **7.7.2 Long Term Data Storage.** A *STRONG STAR Repository* has been approved by the UTHSCSA
410 (HSC20100475H) IRB to enable the *STRONG STAR Consortium* to store specimens and data for future use. The
411 *STRONG STAR Repository* is a large comprehensive database of information, biological specimens and
412 neuroimages related to the identification, assessment, and treatment of posttraumatic stress disorder (PTSD),
413 insomnia, pain, and related behavioral health conditions. All information entered into the *STRONG STAR Repository*
414 will be extracted from primary datasets collected as part of IRB-approved studies, including this study, being
415 conducted and /or supported in collaboration with the UTHSCSA *STRONG STAR Consortium*. Study databases are
416 established and maintained by the Data Management and Biostatistics Core of the *STRONG STAR Consortium*. A
417 unique, sequential alpha-numeric *STRONG STAR ID* will be assigned to each participant at the time of recruitment
418 into this study. However, all Repository data will be identified with a different code number that can be cross linked to
419 the original study code only through records maintained by the *STRONG STAR Data Management and Biostatistics*
420 Core. At the conclusion of this study, participants who signed the consent to have their data placed in the *STRONG*
421 *STAR Repository* will be maintained under the UTHSCSA IRB-approved Repository protocol. For participants who
422 decline participation in the *STRONG STAR Repository*, at the conclusion of the study their data will be de-identified
423 and the data maintained in the Repository without identifiers.
424

425 **8.0 RISKS/BENEFITS ASSESSMENT**

426 **8.1 Risks.**

427 **Likely but not Serious (expected to occur in more than 1 in 5 participants):**

428

- 429 • Participating in mental health treatment and research might increase some symptoms and increase the risk
430 of feeling emotionally uncomfortable in the short term, which might increase the desire for suicide
431 temporarily. This increase is usually not severe, however, and does not last long. Preliminary work with

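### The 80% power in Section 7.4.1 assumes a one-tailed .05 test that Section 7.4.3 never adopts; if that 80% is right, a two-sided test of one contrast has about 70%

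*Combined protocol and SAP*

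**What the plan says.** **Section 7.4.1 (sample size).** The total of 124 (62 per group) comes from repeated-measures power software. The stated inputs are "a quadratic design matrix for the time effect, a 1-tailed alpha" and then "level of .05, desired power of .80", with "equal sized treatment groups at baseline", "an overall expected 15% attrition rate", a stationary AR(1) error correlation of .30, and d = .35 at the last assessment. No reason is given for using one tail.

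**Section 7.4.3 (analyses).** Mixed models carry fixed effects for treatment, time and their interaction. The interaction is said to capture differences in change over "time between the groups; as such it is the effect of substantive interest in each of the models that will be examined". Between- and within-group contrasts are described as a way to explore an interaction already found significant. The section gives no alpha, no number of tails and no primary contrast.

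**Section 3 (aims).** The aims ask an open question about whether WET-S reduces the outcomes. The hypotheses under them are directional, for benefit only.

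**Section 8.1 (risks).** Among risks expected in more than one participant in five, the protocol lists a greater chance "of feeling emotionally uncomfortable in the short term, which might increase the desire for suicide" for a time. It adds that any such rise is usually mild and short-lived. The same list includes an initial rise in PTSD symptoms from talking or writing about the trauma.

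**Section 5 (background).** WET has not yet been tested in patients hospitalised for high suicide risk.

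**The concern.** A power figure belongs to a particular test. Here the sample-size section and the analysis section do not describe the same one. A one-tailed alpha makes sense only for a single contrast with a direction. An interaction with quadratic time has two parameters, linear and quadratic. An interaction with four assessments treated as categories has three. Tested as a whole, neither has a direction, and standard mixed-model output tests even a single coefficient two-sided unless the analyst specifies otherwise.

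Two things follow. First, if the trial is analysed in the ordinary way, its power for d = .35 is below the stated 80%. Second, because sidedness is not fixed in advance, a reader cannot tell whether a claim of benefit would carry a 2.5% or a 5% chance of being false. The direction matters in this trial. The treatment is new to suicidal inpatients, and by the protocol's own account some worsening is possible. A result in the unfavourable direction should have a pre-stated interpretation.

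**Working it through.** **Inputs, all from Section 7.4.1:** one-tailed alpha .05, power .80, d = .35 at the final assessment, N = 124 (62 per group), 15% attrition, AR(1) correlation .30. The Abstract gives four assessments: pre-treatment, post-treatment, 1 month and 4 months. Not given: the number of visits entered in the software, the effect at earlier visits, the timing of dropout, and the contrast tested.

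**Step 1. Can N = 124 be reproduced?** Not from the inputs given.
- Plain comparison at the final visit: n per arm = 2 × (1.645 + 0.842)² / 0.35² = 2 × 6.183 / 0.1225 = 100.9, so 101. Dividing 100.9 by 0.85 for attrition gives 118.8, so 119 per arm or 238 in total.
- Group-by-time models with AR(1) .30, three or four visits and 15% attrition: about 131 to over 400 in total, depending on the assumed effect profile and contrast.
- Some settings come close but do not match the stated inputs. Five visits with the full effect from the first post-baseline visit, linear time and 15% attrition give 123. Four equally spaced visits with the same effect profile, linear time and no attrition give 118 to 125.

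The 80% is therefore neither confirmed nor refuted. The next steps take it as given.

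**Step 2. Noncentrality implied by the plan.** For 80% power at one-tailed .05:

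δ = z(.95) + z(.80) = 1.645 + 0.842 = 2.486 (from unrounded values)

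Visits, correlation and attrition are all absorbed in δ, so the conversion below does not depend on them.

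**Step 3. Two-sided .05 test of the same single contrast.**
- Power = Φ(2.486 − 1.960) = Φ(0.526) = 0.701.
- Effect detectable with 80% power: d = .35 × (1.960 + 0.842) / 2.486 = .35 × 1.127 = .394.
- For scale, 80% two-sided power at d = .35 would need 124 × 1.127² = 124 × 1.2695 = 157.4, or about 158 in total (79 per group).

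**Step 4. Omnibus interaction at the same noncentrality.** λ = 2.486² = 6.18, with a noncentral chi-square at alpha .05.

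| Test | Critical value | Power |
|---|---|---|
| 1 df, two-sided | 3.84 | 70% |
| 2 df | 5.99 | 60% |
| 3 df | 7.81 | 53% |

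The 2- and 3-df rows assume that the whole true effect lies along the contrast that gave δ. An effect with further components would raise λ and the power.

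**Step 5. Sensitivity to the unverified 80%.** On the plain final-visit reading, 62 per arm gives δ = .35 × √(62/2) = 1.949, so power is 62% one-tailed and 50% two-sided. With 15% attrition (52.7 per arm), δ = .35 × √(52.7/2) = 1.797, and power is 56% and 43.5%.

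**The case against.** The strongest reply has four parts.

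*The one-tailed choice is disclosed and fits directional hypotheses.* It is disclosed, and it is a debatable design choice rather than a hidden error. But a directional hypothesis does not by itself justify a one-tailed test; the opposite result would have to be impossible or of no interest. More to the point, the choice is not carried into the analysis section.

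*The risk text does not show that WET-S is expected to do harm.* This stands. A reader might infer from Section 8.1 that the protocol predicts a rise in suicidality in the WET-S arm. It does not. The statement about suicidal desire concerns taking part in mental health treatment and research generally, is hedged, describes a temporary effect, and is followed by a remark that distress typically falls straight afterwards. The power target is at 4 months, and a short rise common to both arms says little about that contrast. The item on writing about trauma is closer to WET-S, but it too concerns an initial increase. What remains is that worsening is plausible in a population where this treatment is untested.

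*The plan does not rule out a test for harm.* This also stands. A reader might infer that the trial cannot report worsening, or accepts a 5% chance of a false benefit claim. Both would hold only if the analyses were one-tailed, and one tail appears only as a sample-size input. Safety is also watched through a monitoring plan, repeated ratings of mood and suicidal intent, an independent monitor who may stop the study, and adverse event reporting. None of these is a randomised comparison of suicidality, but unfavourable results are not blocked from view.

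*The 70% is not a firm figure.* Correct. It presumes the stated 80% and a single contrast, neither of which the documents secure.

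**Conclusion.** The point holds as a mismatch between the power statement and the planned analysis. Section 7.4.1 claims 80% for a one-tailed test; Section 7.4.3 describes an interaction test with no tail, no alpha and no named contrast, which is ordinarily non-directional.

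If the stated 80% is right, N = 124 gives about 70% two-sided power for d = .35 on one contrast, a loss of about 10 percentage points, and 80% for about d = .39. An omnibus test at the same noncentrality gives about 60% (2 df) or 53% (3 df). These are conversions of the plan's own figure, not an independent estimate of its power. It would be wrong to conclude that the trial has been shown to have 70% power: the 80% could not be reproduced, and the plain final-visit reading gives less.

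This should be corrected, but the trial remains runnable.

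**What to change.** **In 7.4.3:** name the primary group-by-time contrast (for example, the between-arm difference in change from pre-treatment to 4 months, since 7.4.1 places the effect at the final assessment). State that it is tested two-sided at .05 and reported with a 95% interval, so that a result in either direction can be read.

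**In 7.4.1:** rerun the power calculation for that contrast and report every input, including the number of visits, the assumed effect at each visit and the attrition pattern. Then restate the power for N = 124. Until the rerun is done, about 70% for d = .35 (80% for about d = .39) may be quoted only as conditional on the existing calculation being right.

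**Cost:** one rerun of the software and some rewording. Enrolment does not change. The downside is a less favourable stated power; keeping 80% two-sided at d = .35 would take about 158 participants on the same conversion, which is not proposed here.
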